#### Treatment Planning System Output

RT treatment plans including CT, structures, dose and plan files. These items are included in the digital plan.

Digitally reconstructed radiographs (DRR) for each treatment field, showing the collimator and beam aperture. Submission of DRR's is not required for IMRT/VMT plans.

Treatment planning system summary report that includes the monitor unit calculations, beam parameters, calculation algorithm, and volume of interest dose statistics.

#### Supportive Data

Copies and reports of all imaging studies used to define the target volume.

Prescription sheet for entire treatment.

#### Forms

RT-1 Dosimetry Summary Form

Motion Management Reporting Form

**Within 21 days of the completion of radiotherapy, the following data shall be submitted for all patients:**

IGRT Data -- Volumetric IGRT data in DICOM format from each of the 3 treatment fractions, including the DICOM spatial registration file (REG file) for each fraction if available from your image guidance system.

The RT-2 Radiotherapy Total Dose Record Form

A copy of the patient's radiotherapy record including the prescription, and the daily and cumulative doses to all required areas.

Documentation listed above showing any modifications from the original submission.

Supportive data and forms may be included with the transmission of the digital RT data or submitted separately via e-mail to [[contact]](mailto:[contact]).

Questions regarding the dose calculations or documentation should be directed to:

Protocol Dosimetrist  
IROC Rhode Island QA Center  
[contact]  
Email: [[contact]](mailto:[contact])

### **7.1.9 Compliance Criteria**

Definitions of Deviations in Dose to Target Volumes

Per Protocol: The dose to the target volume meets the "Per Protocol" requirements specified in Tables 1.6 and 1.8.

Variation Acceptable: The dose to the target volume falls within the "Variable Acceptable" range specified in Tables 1.6 and 1.8.

Deviation Unacceptable: The dose to the target volume falls outside the "Variable Acceptable" range specified in Tables 1.6 and 1.8.

Definitions of Deviations in Dose to Normal Structures

Per Protocol: The dose to normal structures meets the constraints in Table 1.9.

Variation Acceptable: The dose to normal structures falls within the "Variable Acceptable" range specified in Table 1.9 & 1.10.

Deviation Unacceptable: The dose to normal structures falls outside the "Variable Acceptable" range specified in Table 1.9 & 1.10.

Definitions of Deviations in Volumes Drawn

Per protocol: All specified contouring volumes are drawn as specified in the protocol.

Variation Acceptable: Delineation of specified contouring volumes deviates from protocol guidelines but the protocol intended volumes are adequately covered by the prescribed doses.

Deviation Unacceptable: Delineation of specified contouring volumes deviates significantly from protocol guidelines and the protocol intended volumes are not adequately covered by the prescribed doses

## **8.0 DOSE AND TREATMENT MODIFICATIONS**

Adverse events (both non-serious and serious) associated with pembrolizumab (MK-3475) exposure after radiation may represent an immunologic etiology. These adverse events may occur shortly after the first dose or several months after the last dose of treatment. pembrolizumab (MK-3475) must be withheld for drug-related toxicities and severe or life-threatening AEs as per below. See Section 5.6.1 and Events of Clinical Interest Guidance Document for supportive care guidelines, including use of corticosteroids.

**Table 2 Dose Modification Guidelines for Drug-Related Adverse Event**

General instructions:				
1. Severe and life-threatening irAEs should be treated with IV corticosteroids followed by oral steroids. Other immunosuppressive treatment should begin if the irAEs are not controlled by corticosteroids. 2. Pembrolizumab must be permanently discontinued if the irAE does not resolve or the corticosteroid dose is not $\leq 10$ mg/day within 12 weeks of the last pembrolizumab treatment. 3. The corticosteroid taper should begin when the irAE is $\leq$ Grade 1 and continue at least 4 weeks. 4. If pembrolizumab has been withheld, pembrolizumab may resume after the irAE decreased to $\leq$ Grade 1 after corticosteroid taper.				
irAEs	Toxicity grade (CTCAE V5.0)	Action with pembrolizumab	Corticosteroid and/or other therapies	Monitoring and follow-up
Pneumonitis	Grade 2	Withhold	
 
Administer corticosteroids (initial dose of 1 - 2 mg/kg prednisone or equivalent) followed by taper
 
Add prophylactic antibiotics for opportunistic infections
 
	
 
Monitor participants for signs and symptoms of pneumonitis
 
Evaluate participants with suspected pneumonitis with radiographic imaging and initiate corticosteroid treatment
 

	Recurrent Grade 2, Grade 3 or 4	Permanently discontinue		
Diarrhea / Colitis	Grade 2 or 3	Withhold	
 
Administer corticosteroids (initial dose of 1 - 2 mg/kg prednisone or equivalent) followed by taper
 
	
 
Monitor participants for signs and symptoms of enterocolitis (ie, diarrhea, abdominal pain, blood or mucus in stool with or without fever) and of bowel perforation (ie, peritoneal signs and ileus)
 
Participants with <math>\geq</math>Grade 2 diarrhea suspecting colitis should consider GI consultation and performing endoscopy to rule out colitis
 
Participants with diarrhea/colitis should be advised to drink liberal quantities of clear fluids. If sufficient oral fluid intake is not feasible, fluid and electrolytes should be
 

	Recurrent Grade 3 or Grade 4	Permanently discontinue		

				substituted via IV infusion
AST or ALT elevation or Increased Bilirubin	Grade 2 a	Withhold	
 
Administer corticosteroids (initial dose of 0.5 - 1 mg/kg prednisone or equivalent) followed by taper
 
	
 
Monitor with liver function tests (consider weekly or more frequently until liver enzyme value returned to baseline or is stable)
 

	Grade 3 b or 4 c	Permanently discontinue	
 
Administer corticosteroids (initial dose of 1 - 2 mg/kg prednisone or equivalent) followed by taper
 
	
Type 1 diabetes mellitus (T1DM) or Hyperglycemia	New onset T1DM or Grade 3 or 4 hyperglycemia associated with evidence of $\beta$ -cell failure	Withhold d	
 
Initiate insulin replacement therapy for participants with T1DM
 
Administer anti-hyperglycemic in participants with hyperglycemia
 
	
 
Monitor participants for hyperglycemia or other signs and symptoms of diabetes
 

Hypophysitis	Grade 2	Withhold	
 
Administer corticosteroids and initiate hormonal replacements as clinically indicated
 
	
 
Monitor for signs and symptoms of hypophysitis (including hypopituitarism and adrenal insufficiency)
 

	Grade 3 or 4	Withhold or permanently discontinue d		
Hyperthyroidism	Grade 2	Continue	
 
Treat with non-selective beta-blockers (eg, propranolol) or thionamides as appropriate
 
	
 
Monitor for signs and symptoms of thyroid disorders
 

	Grade 3 or 4	Withhold or permanently discontinue d		
Hypothyroidism	Grade 2, 3, 4	Continue	
 
Initiate thyroid replacement hormones (eg, levothyroxine or
 
	
 
Monitor for signs and symptoms of thyroid disorders
 

			liothyronine) per standard of care	
Nephritis: grading according to increased creatinine or acute kidney injury	Grade 2	Withhold	
 
Administer corticosteroids (prednisone 1 – 2 mg/kg or equivalent) followed by taper
 
	
 
Monitor changes of renal function
 

	Grade 3 or 4	Permanently discontinue		
Myocarditis	Grade 1 or 2	Withhold	
 
Based on severity of AE administer corticosteroids
 
	
 
Ensure adequate evaluation to confirm etiology and/or exclude other causes
 

	Grade 3 or 4	Permanently discontinue		
All Other immune-related AEs	Persistent Grade 2	Withhold	
 
Based on severity of AE administer corticosteroids
 
	
 
Ensure adequate evaluation to confirm etiology or exclude other causes
 

	Grade 3	Withhold or discontinue based on the event e		
	Recurrent Grade 3 or Grade 4	Permanently discontinue		

a AST/ALT: >3.0 - 5.0 x ULN if baseline normal; >3.0 - 5.0 x baseline, if baseline abnormal; bilirubin:>1.5 - 3.0 x ULN if baseline normal; >1.5 - 3.0 x baseline if baseline abnormal
 
b AST/ALT: >5.0 to 20.0 x ULN, if baseline normal; >5.0 - 20.0 x baseline, if baseline abnormal; bilirubin:>3.0 - 10.0 x ULN if baseline normal; >3.0 - 10.0 x baseline if baseline abnormal
 
c AST/ALT: >20.0 x ULN, if baseline normal; >20.0 x baseline, if baseline abnormal; bilirubin: >10.0 x ULN if baseline normal; >10.0 x baseline if baseline abnormal
 
d The decision to withhold or permanently discontinue pembrolizumab is at the discretion of the investigator or treating physician. If control achieved or ≤ Grade 2, pembrolizumab may be resumed.
 
e Events that require discontinuation include but are not limited to: Guillain-Barre Syndrome, encephalitis, Stevens-Johnson Syndrome and toxic epidermal necrolysis.
				

Dosing interruptions are permitted in the case of medical / surgical events or logistical reasons not related to study therapy (e.g., elective surgery, unrelated medical events, patient vacation, and/or holidays). Subjects should be placed back on study therapy within 3 weeks of the scheduled interruption, unless otherwise discussed with the Principal Investigator. The reason for interruption should be documented in the patient's study record.

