#### **8.1.3 Type 1 diabetes mellitus (if new onset, including diabetic ketoacidosis [DKA]) or ≥ Grade 3 Hyperglycemia, if associated with ketosis (ketonuria) or metabolic acidosis (DKA)**

- For T1DM or Grade 3-4 Hyperglycemia
- Insulin replacement therapy is recommended for Type I diabetes mellitus and for Grade 3-4 hyperglycemia associated with metabolic acidosis or ketonuria.
- Evaluate patients with serum glucose and a metabolic panel, urine ketones, glycosylated hemoglobin, and C-peptide.

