### 8.1.5 Hyperthyroidism or Hypothyroidism:

Thyroid disorders can occur at any time during treatment. Monitor patients for changes in thyroid function (at the start of treatment, periodically during treatment, and as indicated based on clinical evaluation) and for clinical signs and symptoms of thyroid disorders.

- Grade 2 hyperthyroidism events (and Grade 2-4 hypothyroidism):
- In hyperthyroidism, non-selective beta-blockers (e.g. propranolol) are suggested as initial therapy.
- In hypothyroidism, thyroid hormone replacement therapy, with levothyroxine or liothyronine, is indicated per standard of care.
- Grade 3-4 hyperthyroidism
- Treat with an initial dose of IV corticosteroid followed by oral corticosteroids. When symptoms improve to Grade 1 or less, steroid taper should be started and continued over no less than 4 weeks. Replacement of appropriate hormones may be required as the steroid dose is tapered.

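### Steroid instructions for grade 3-4 hyperthyroidism conflict, and the reach of Table 2's general steroid and resumption rules over other endocrine events is not stated

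*Combined protocol and SAP*

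**What the plan says.** Table 2 in Section 8.0 opens with four general instructions. The first covers steroids: "Severe and life-threatening irAEs should be treated with IV corticosteroids followed by oral steroids". It names no event to which it does not apply. The fourth lets withheld pembrolizumab restart once the event is at grade 1 or lower after a steroid taper.

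The rows then give treatment event by event, in a column for corticosteroids and other therapies:

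- Hyperthyroidism, with one entry spanning grade 2 and grade 3 or 4: "Treat with non-selective beta-blockers (eg, propranolol) or thionamides as appropriate".
- Hypothyroidism, grades 2 to 4: thyroid hormone replacement, with pembrolizumab continued.
- New-onset type 1 diabetes (T1DM), or grade 3-4 hyperglycemia with signs of β-cell failure: "Initiate insulin replacement therapy for participants with T1DM", with anti-hyperglycemic treatment for hyperglycemia.
- Hypophysitis: "Administer corticosteroids and initiate hormonal replacements as clinically indicated".

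Footnote d is attached to the T1DM/hyperglycemia row and to the grade 3-4 entries for hypophysitis and hyperthyroidism. It leaves withholding or stopping to the physician and permits resumption once the event is controlled or at grade 2 or lower.

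Section 8.1 covers the same events again. Section 8.1.5 says of grade 3-4 hyperthyroidism: "Treat with an initial dose of IV corticosteroid followed by oral corticosteroids". For grade 2-4 hypothyroidism it gives hormone replacement. Section 8.1.3 says: "Insulin replacement therapy is recommended for Type I diabetes mellitus and for Grade 3-4 hyperglycemia associated with metabolic acidosis or ketonuria". Section 8.1.4 gives IV then oral steroids for grade 3-4 hypophysitis.

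The opening paragraph of Section 8.0 refers sites to a Section 5.6.1, and to a separate guidance document on events of clinical interest, for supportive care including steroid use.

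**The concern.** A site managing grade 3-4 hyperthyroidism finds systemic steroids in two places and none in the row written for that event. No text ranks the general instructions, the rows and Section 8.1. For grade 3-4 hypothyroidism and T1DM/hyperglycemia, a site cannot tell whether instruction 1 applies at all.

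The choice also affects later decisions on study drug. Under general instruction 2, "Pembrolizumab must be permanently discontinued if the irAE does not resolve or the corticosteroid dose is not" at or below 10 mg/day within 12 weeks of the last pembrolizumab treatment, so starting steroids brings a stopping criterion into play. With two resumption thresholds, the same patient could be cleared to restart under one rule and not under the other. Steroid use and drug exposure could then vary with the paragraph a site happened to read.

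These events are foreseeable here: hyperthyroidism and hypothyroidism are solicited adverse events in Section 9.1, and the study calendar calls for TSH on day 1 of each cycle.

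**Working it through.** There is no planned figure to reproduce. The check sets the three sources side by side for each endocrine event at grade 3-4.

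| Event | General instruction 1 | Table 2 row | Section 8.1 |
|---|---|---|---|
| T1DM / hyperglycemia | IV then oral steroid | insulin or anti-hyperglycemic; no steroid listed | 8.1.3: insulin; no steroid listed |
| Hypophysitis | IV then oral steroid | steroid plus hormones as indicated | 8.1.4: IV then oral steroid |
| Hyperthyroidism | IV then oral steroid | beta-blocker or thionamide; no steroid listed | 8.1.5: IV then oral steroid |
| Hypothyroidism | IV then oral steroid | thyroid replacement; no steroid listed | 8.1.5: thyroid replacement; no steroid listed |

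Counts:

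- Row differs from instruction 1: 3 of 4 (T1DM/hyperglycemia, hyperthyroidism, hypothyroidism).
- Row differs from its own Section 8.1 text on steroids: 1 of 4 (hyperthyroidism).
- All three sources compatible on steroids: 1 of 4 (hypophysitis, where the row omits only the route).

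Next, can an unstated order of precedence remove the problem?

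1. Suppose instruction 1 adds to every row. The hyperthyroidism row and Section 8.1.5 then fit together. But grade 3-4 hypothyroidism and T1DM/hyperglycemia acquire a steroid course that neither their rows nor Sections 8.1.5 and 8.1.3 mention.
2. Suppose each row replaces instruction 1. Hypothyroidism and T1DM/hyperglycemia become consistent, but the hyperthyroidism row then stands against Section 8.1.5.
3. Suppose Section 8.1 decides. That gives one answer per event, but no text says so, and Section 8.1 describes its measures as suggested.

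The first two readings each leave a conflict, and none of the three is stated. The list shows the gap; it is not a choice among the readings.

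For resumption, instruction 4 sets grade 1 or lower after a taper, and footnote d sets control or grade 2 or lower. Both apply on their face to the three entries carrying footnote d, including grade 3-4 hypophysitis. An event that has settled at grade 2 meets footnote d and fails instruction 4. For hypothyroidism the row continues the drug, so neither rule comes into play under that row.

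Last, the cross-reference. Section 5.0 is the Study Calendar, and neither it nor the table of contents shows a Section 5.6.1. The pointer therefore cannot serve as a tie-breaker.

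**The case against.** The strongest reply is that these are guidelines, not orders. Table 2 is titled as such, and Section 8.1 offers suggested measures, where appropriate, as the investigator judges necessary. The rows that list no steroid do not forbid one, and beta-blockers or thionamides can be read as given alongside steroids. For hypothyroidism and T1DM/hyperglycemia the two event-specific texts agree, so what remains there is a general line beside specific rows. The guidance document named in Section 8.0 may settle the matter; it is not part of the documents reviewed, so that cannot be determined. Finally, the study is closed to new accrual and both arms receive pembrolizumab.

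Much of this stands, and it rules out several stronger readings that a reader might infer:

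- That Table 2 gives no steroids for endocrine events as a class. The hypophysitis row does, and Section 8.1.4 agrees.
- That patients with the same event receive opposite treatment. Silence in a row is not a prohibition; the supportable word is inconsistent.
- That the hyperglycemia triggers contradict each other because Table 2 refers to β-cell failure and Section 8.1.3 to ketosis or acidosis. The first sits in the column that governs withholding the drug and the second introduces insulin and work-up. Different wording for different actions is weak evidence of conflict.
- That the minimum 4-week taper against a 21-day cycle (28/21 = 1.3) means a missed cycle. Footnote d offers another route to resumption for T1DM/hyperglycemia and grade 3-4 hyperthyroidism, and the hypothyroidism row continues the drug.

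The reply does not remove the hyperthyroidism conflict, the unstated scope of instruction 1 or the two resumption thresholds. Calling Section 8.1 suggested also does nothing for the mismatch inside Table 2, between instruction 1 and the table's own rows.

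**Conclusion.** The point holds in a limited form. There is one direct inconsistency on steroids (grade 3-4 hyperthyroidism: the row against Section 8.1.5 and instruction 1), one gap in scope (instruction 1 for grade 3-4 hypothyroidism and T1DM/hyperglycemia), and one pair of differing resumption rules (instruction 4 against footnote d). The broken pointer in Section 8.0 removes one place where a site might have looked for an answer.

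No patient count is claimed, because the documents give no rate of grade 3-4 endocrine events for this trial, and no missed-cycle figure is claimed. Sample size, power and type I error are unaffected. With accrual closed, the practical reach is to patients still on treatment or being managed for late immune-related events, which Section 8.0 says may appear months after the last dose. The conclusion rests on the protocol text alone and assumes that the separate guidance document does not already state which instruction governs. No view is taken on which clinical rule is right.

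**What to change.** The sponsor's safety team should reconcile these passages so that each endocrine event and grade has one treatment instruction and one resumption rule:

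- Table 2 general instructions 1 and 4;
- the Table 2 rows for hyperthyroidism, hypothyroidism and T1DM/hyperglycemia;
- Table 2 footnote d, including its use on the grade 3-4 hypophysitis entry;
- Sections 8.1.3 and 8.1.5.

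The revised text should say explicitly whether instruction 1 covers grade 3-4 hypothyroidism and T1DM/hyperglycemia. The Section 8.0 reference to Section 5.6.1 should be corrected to a section that exists. The clinical content is for the safety team to decide. The cost is protocol wording in an amendment, with no change to the design or the analysis.

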### 8.1 Supportive Care

Subjects should receive appropriate supportive care measures as deemed necessary by the treating investigator. Suggested supportive care measures for the management of adverse events with potential immunologic etiology are outlined below. Where appropriate, these guidelines include the use of oral or intravenous treatment with corticosteroids as well as additional anti-inflammatory agents if symptoms do not improve with administration of corticosteroids. Note that several courses of steroid tapering may be necessary as symptoms may worsen when the steroid dose is decreased.

For each disorder, attempts should be made to rule out other causes such as metastatic disease or bacterial or viral infection, which might require additional supportive care. The treatment guidelines are intended to be applied when the investigator determines the events to be related to pembrolizumab (MK-3475) and/or Bifidobacterium dietary supplement.

Note: if after the evaluation the event is determined not to be related, the investigator does not need to follow the treatment guidance (as outlined below).

It may be necessary to perform conditional procedures such as bronchoscopy, endoscopy, or skin photography as part of evaluation of the event.

#### **8.1.1 Pneumonitis:**

- For Grade 2 events, treat with systemic corticosteroids. When symptoms improve to Grade 1 or less, steroid taper should be started and continued over no less than 4 weeks.
- For Grade 3-4 events, immediately treat with intravenous steroids. Administer additional anti-inflammatory measures, as needed.
- Add prophylactic antibiotics for opportunistic infections in the case of prolonged steroid administration.

#### **8.1.2 Diarrhea/Colitis:**

Subjects should be carefully monitored for signs and symptoms of enterocolitis (such as diarrhea, abdominal pain, blood or mucus in stool, with or without fever) and of bowel perforation (such as peritoneal signs and ileus).

- All subjects who experience diarrhea/colitis should be advised to drink liberal quantities of clear fluids. If sufficient oral fluid intake is not feasible, fluid and electrolytes should be substituted via IV infusion. For Grade 2 or higher diarrhea, consider GI consultation and endoscopy to confirm or rule out colitis.
- For Grade 2 diarrhea/colitis, that persists greater than 3 days, administer oral corticosteroids.
- For Grade 3 or 4 diarrhea/colitis, that persists > 1 week, treat with intravenous steroids followed by high dose oral steroids.
- When symptoms improve to Grade 1 or less, steroid taper should be started and continued over no less than 4 weeks.

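### Section 8.1.2 suggests IV steroids for grade 3-4 diarrhea/colitis only after more than a week of persistence, while Table 2 sets no such condition and nothing says which applies

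*Combined protocol and SAP*

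**What the plan says.** Section 8.1.2 has two steroid triggers for diarrhea/colitis. For the milder event: "For Grade 2 diarrhea/colitis, that persists greater than 3 days, administer oral corticosteroids". For the more severe event: "For Grade 3 or 4 diarrhea/colitis, that persists > 1 week, treat with intravenous steroids followed by high dose oral steroids". It gives no other instruction to start steroids at grade 3 or 4. Section 8.1 describes these measures as suggested, leaves care to the investigator's judgment, and applies the guidance to events the investigator considers related to pembrolizumab.

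Table 2 in Section 8.0 also covers drug-related events. Its first general instruction reads: "Severe and life-threatening irAEs should be treated with IV corticosteroids followed by oral steroids". Its diarrhea/colitis row reads: "Administer corticosteroids (initial dose of 1 - 2 mg/kg prednisone or equivalent) followed by taper". Neither statement depends on how long the event has lasted.

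Section 8.0 also sends sites to a Section 5.6.1 and to an external guidance document for supportive care, including corticosteroids. Section 5 of this protocol is the study calendar and has no 5.6.1. The external document is not part of the material reviewed.

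**The concern.** Read as written, 8.1.2 attaches the longer persistence condition to the more severe event. A site with a grade 3 or 4 case finds steroids tied to more than a week of symptoms in one place, and directed without any duration condition in another. The protocol does not rank the two texts.

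What is at stake is the care of individual patients. The nursing guidelines in Section 10.2 warn that diarrhea on this drug can be severe and lead to colonic perforation, and say in general terms that most side effects reverse with prompt corticosteroids. Those remarks set no start time for colitis, so they are context and not evidence for a particular rule. Nothing here bears on the comparison of the arms, the error rates or the stopping rule in Section 13.5.

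**Working it through.** The plan states no figure to reproduce, so the check is a comparison of texts and a count.

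**1. Triggers within 8.1.2.**
- Grade 2: oral steroids after more than 3 days.
- Grade 3-4: IV then high-dose oral steroids after more than 1 week, that is, more than 7 days.
- The thresholds differ by 7 − 3 = 4 days, a ratio of 7/3 = 2.3. The two triggers lead to different treatments (oral against IV plus high-dose oral), so this describes the ordering. It is not a like-for-like delay and does not measure harm.

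**2. Table 2 on the same events.**
- General instruction 1 (severe and life-threatening events): IV then oral steroids, no persistence condition.
- Diarrhea/colitis row: 1-2 mg/kg prednisone or equivalent, then taper, no persistence condition.
- Table 2 does use persistence as a qualifier where its authors wanted one: the row for all other immune-related events has "Persistent Grade 2". The colitis row has no such qualifier.
- Table 2 gives no start time, so no difference in days between it and 8.1.2 can be calculated.

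**3. How firm the Table 2 support is, by grade.** In the text as extracted, the colitis steroid cell sits beside grades 2 and 3, and the cell beside recurrent grade 3 or grade 4 is empty. This may be a merged cell. Grade 3 is therefore covered by the row and by instruction 1. Grade 4 rests on instruction 1, which is weaker support because not every row follows it. The hyperthyroidism row says "Treat with non-selective beta-blockers (eg, propranolol) or thionamides as appropriate" and names no steroid, although 8.1.5 says of grade 3-4 hyperthyroidism: "Treat with an initial dose of IV corticosteroid followed by oral corticosteroids".

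**4. Is a wait usual in Section 8.1?** Counting 8.1.1 to 8.1.7:

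| Instruction | Subsections that give one | With a persistence condition |
|---|---|---|
| Steroids at grade 3-4 | 8.1.1, 8.1.2, 8.1.4, 8.1.5 (hyperthyroidism), 8.1.6, 8.1.7 = 6 | 8.1.2 only: 1 of 6 |
| Steroids at grade 2 | 8.1.1, 8.1.2, 8.1.4, 8.1.6, 8.1.7 = 5 | 8.1.2 only: 1 of 5 |

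Section 8.1.3 (diabetes) gives no steroid instruction. For grade 3-4 pneumonitis, 8.1.1 asks for IV steroids immediately.

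**5. Precedence.** Nothing in Sections 8.0, 8.1, 8.2 or the nursing guidelines says whether Table 2 or 8.1.2 governs.

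**6. Reach.** The number affected is bounded only by 0 and the maximum accrual of 100 in Section 13.3.1; this is a bound, not an estimate. Accrual is permanently closed and treatment is capped at two years. Section 8.0 notes that events may appear several months after the last dose. The documents do not say how many patients remain on treatment.

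**The case against.** The strongest reply is that 8.1.2 tells nobody to withhold steroids. It is suggested care, subject to the investigator's judgment, and it does not bar earlier treatment. That stands, and it limits the point to inconsistent wording.

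A reader might infer that the whole week falls after the event has been judged drug-related. The documents do not support this. Attribution decides when the guidance applies, while persistence is naturally read as running from onset. Part or all of the week may overlap the work-up that 8.1 and 8.1.2 describe: excluding infection, GI consultation and endoscopy. This overlap does not, however, explain why the more severe grades carry the longer condition.

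A reader might also infer that 8.1.2 contradicts Table 2, or that waiting breaches it. That is not shown either, because Table 2 gives no start time. For grade 3 the texts can be read together: start the Table 2 dose, whose route the row leaves open, and treat the 8.1.2 bullet as IV escalation for persistent disease. General instruction 1, which names IV steroids for severe events, strains that reading, and nothing tells a site to adopt it.

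The external guidance document may settle the timing. And other protections carry no wait: Table 2 withholds pembrolizumab at grade 2 or 3 and stops it for recurrent grade 3 or for grade 4. Section 8.1.2 provides fluids, monitoring for perforation and consideration of GI consultation without delay. These points reduce the consequence but leave the two texts unreconciled.

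**Conclusion.** The point holds as a patient-safety wording inconsistency. Section 8.1.2 ties IV steroids for grade 3-4 diarrhea/colitis to more than a week of persistence, with no earlier steroid instruction for those grades. Table 2 sets no such condition, and the protocol does not rank them. Section 8.1.2 is the only one of six grade 3-4 steroid instructions in 8.1.1 to 8.1.7 to add a wait.

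This rests on the ordinary reading of the persistence clause as a condition for starting, and, for grade 4, on general instruction 1 of Table 2. The documents do not establish a delay of any given length for any patient, a breach of Table 2, or any effect on trial inference. The number affected is unknown and may be small. The correction is worth making because it is nearly free and the bullet, followed as written, gives the less safe result.

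**What to change.** In the grade 3-4 bullet of 8.1.2, delete the clause requiring more than one week of persistence, so that the bullet matches general instruction 1 of Table 2. Because this changes clinical guidance, the clinical team should sign it off. Send a notice to sites with patients on treatment or recently off it.

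Optionally, add to 8.1.2 a sentence saying that, for diarrhea/colitis only, Table 2 governs corticosteroid use where the two differ. It should not extend to the rest of 8.1, because it would then override the grade 3-4 hyperthyroidism steroids in 8.1.5.

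Two related items are separate. Whether the three-day condition at grade 2 should stay is a query for the clinical team. It should be answered before the precedence sentence is added; if the condition is kept, the colitis row of Table 2 should state it for grade 2 only. The reference to Section 5.6.1 in Section 8.0 is a clerical correction; Section 8.1 is the likely target, to be confirmed.

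The cost is a few wording edits and a site notice. Design, data collection and analysis do not change.
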